**Table 16-8 Moderate inhibitors and inducers of CYP3A4\***

CYP3A4	Concomitant Medication Name	Action
Moderate inhibitors of CYP3A4	aprepitant, casopitant, cimetidine, ciprofloxacin, crizotinib, cyclosporine, diltiazem, dronedarone, erythromycin, ferula asafetida resin ( herbal product ), fluconazole, isavuconazole, netupitant, schisandra sphenanthera ( herbal product ), tofisopam, verapamil, duvelisib, letermovir, lefamulin, ravuconazole, istradefylline, voxelotor, atazanavir, ritonavir, darunavir, ACT-539313, darunavir, fedratinib, letermovir, GSK2647544, lefamulin, amprenavir, faldaprevir, imatinib, ravuconazole, netupitant, nilotinib, istradefylline, tofisopam, berotralstat, ACT-178882, voxelotor, FK1706	Avoid moderate CYP3A4 inhibitor if alternative available.
Moderate inducers of CYP3A4	semagacestat, efavirenz, tipranavir, ritonavir, dabrafenib, cenobamate, lesinurad, bosentan, thioridazine, rifabutin, metamizole, lorlatinib, nafcillin, talviraline, phenobarbital, lopinavir, sunaprevir, beclabuvir, daclatasvir, modafinil, PF-06282999, pexidartinib, etavirine, elagolix, sotorasib, lersivirine, telotristat ethyl	Avoid moderate CYP3A4 inducer if alternative available.

\* The list is not exhaustive; concomitant medication used for fungal treatment in the list only apply to oral/parenteral medication

**Table 16-9 Strong inhibitors and inducers of CYP3A4**

CYP3A4	Concomitant Medication* Name	Action
Strong inhibitors of CYP3A4	clarithromycin, conivaptan, itraconazole, ketoconazole, mibefradil, nefazodone, posaconazole, telithromycin, troleandomycin, voriconazole, mifepristone, ombitasvir, paritaprevir, ritonavir, dasabuvir, indinavir, tipranavir, cobicistat, danoprevir, elvitegravir, saquinavir, lopinavir, LCL161, josamycin, lonafarnib, posaconazole, grapefruit juice, conivaptan, tucatinib, nefazodone, deritinib, nelfinavir, ribociclib, boceprevir	Avoid strong CYP3A4 inhibitor if alternative available.
Strong inducers of CYP3A4	apalutamide, avasimibe, carbamazepine, enzalutamide, rifampin, mitotane, phenobarbital, phenytoin, rifabutin, St. John's wort (herbal product), lumacaftor, rifapentine, ivosidenib	Discontinue strong CYP3A4 inducer if medically justifiable and closely monitor for potential associated adverse events.

\*Concomitant medication used for fungal treatment in the list only apply to oral/parenteral medication

**Document History – Changes compared to previous final version of SAP**

Date	Time point	Reason for update	Outcome for update	Section and title impacted (Current)
24-Aug-2022	Prior to DB lock	first version	N/A - First version	NA
27-Feb-2025	CCI [REDACTED] [REDACTED] [REDACTED] before final DB lock	

add texts to clarify Bayesian logistic regression being used in case of complete separation; add texts to provide marginal risk difference from logistic regression; clarify primary estimand policy and add sensitivity analysis

add a new supplementary estimand to consider the impact of treatment failure on conclusion CCI [REDACTED] [REDACTED] [REDACTED] [REDACTED]

clarify PD analysis set is used for efficacy analysis; and update the protocol deviation that impacts the analysis sets

resolve inconsistency in describing intercurrent event and on-treatment period; or delete outdated texts

update sample size

add Bayesian logistic regression with MAP prior as supplementary analysis

list AEs of special interest

	

add outputs to provide marginal risk difference; add outputs for sensitivity analysis

add outputs of new estimand; add outputs of fisher exact test

update outputs due to the update of analysis sets

update texts

Update texts

Add outputs for supplementary analysis

NA

	

section 2.5.2 statistical hypothesis, model, and method of analysis; section 2.5.4 Sensitivity analyses

section 2.5.5 Supplementary analyses

section 2.2 Analysis sets & section 5.6 Rule of exclusion criteria of analysis sets

section 1.2.1 Primary estimand(s) and section 2.1: section 1 Introduction

section 1.1 Study design & section 3 Sample size calculation

section 2.5.5 Supplementary analysis

section 2.7.1.1

Date	Time point	Reason for update	Outcome for update	Section and title impacted (Current)
14-May-2025	CCI [REDACTED] [REDACTED] [REDACTED] before final DB lock	

remove Fisher exact test from supplementary analyses

clarify that supplementary estimand 1 and 3 will not be run

remove CTAE grade from table to avoid version conflict

on-treatment period has been modified to align across LOU064 trials within program

clarify the number for MCMC & bootstrap sampling is 10000 for Bayesian method and frequentist method, respectively

adding rules for unscheduled assessments

clarify that some analyses will not be performed because they do not target any objective specified in Protocol

clarify the method to estimate marginal response rates from Bayesian/frequentist logistic regression

clarify that up to and including 3000 mg of peanut protein (instead of 1000 mg, a typo in protocol) will be used to summarize maximum severity of symptoms

	

remove TFLs of Fisher exact test

remove TFLs of supplementary 1 and 3

NA

Update TFLs of safety endpoints

Update TFLs of MCPmod

NA

NA

NA

Update the table summarizing symptom severity

	

Section 2.5.5 Supplementary analyses

Section 2.5.5 Supplementary analyses

Section 2.7.3 Laboratory data

Section 2.7 Safety analyses

Section 2.5.2 Statistical hypothesis model, and method of analysis

Section 2.1 Data analysis general information

Section 2.6.1 Secondary endpoints

Section 2.5.2 Statistical hypothesis, model, and method of analysis

Section 2.6.1 Secondary endpoints

**List of abbreviations**

---

AE	Adverse Event
AESI	Adverse Event of special interest
AIC	Akaike information criterion
ANCOVA	Analysis of Covariance
AUClast; AUCtau	Area under (the) curve up to last time point; for the dosing interval
CCI	
CCI	
BMI	Body mass index
Bpm	Beats per minute
CI	Confidence Interval
CM	Concomitant medication
Cmax	Maximum blood concentration
COVID-19	Coronavirus disease (2019)
CRO	Contract Research Organization
CRF	Case Report Form
CRS	Case Retrieval Strategy
CTCAE	Common terminology criteria for adverse event
CV	Coefficient of Variation
DB(L)	Database (lock)
DBPCFC	Double-Blind Placebo Controlled Food Challenge
CCI	
ECG	ElectroCardioGram
ED	Effective dose
Emax	Maximum effect
EOS	End of study
HMC	Hamiltonian Monte Carlo
IA	Interim Analysis
ICH-GCP	ICH guideline for good clinical practice
IgE	Immunoglobulin E
IgG	Immunoglobulin G
LLN	Lower level of normal
LLOQ	Lower Limit of Quantification
MAR	Missing At Random
CCI	
MedDRA	Medical Dictionary for Drug Regulatory Affairs
MCP-Mod	Multiple Comparison Procedure – Modelling
ML	Maximum Likelihood
MTD	Maximum Tolerated Dose
OFC	Oral food challenge
PK/PD	Pharmacokinetics/Pharmacodynamics
PT	Preferred Term
RAP	Reporting & Analysis Process
SAE	Serious Adverse Event
SAP	Statistical Analysis Plan
SAS	Statistical Analysis System

---

---

SD	Standard Deviation
SMQ	Standardized MedDRA Query
SOC	System Organ Class
SPT	Skin Prick Test
TFLs	Tables, Figures, Listings
CCI	
Tmax	Time to reach maximum blood concentration
ULN	Upper limit of normal
ULOQ	Upper Limit of Quantification
WHO	World Health Organization

---

[figure not shown]

## 1 Introduction

The purpose of this document is to describe the statistical analyses relevant to meeting the objectives mentioned in the version 02 of the Phase 2 study, CLOU064I12201 protocol. All objectives will be covered in this plan with the exception of certain exploratory outputs for biomarkers that will be covered in a separate biomarker analysis plan.

### 1.1 Study design

Figure 1-1 Study Overview

This is a Phase 2 multi-center, randomized, participant- and investigator-blinded, placebo-controlled study to assess the safety and clinical efficacy of four dosing regimens of oral remibrutinib versus placebo (CCI for one month (4-5 weeks); CCI for one month (4-5 weeks); CCI for one month (4-5 weeks); placebo for 3 weeks followed by remibrutinib CCI for 1-2 weeks; and placebo for one month (4-5 weeks) in adult participants with a medically confirmed diagnosis of IgE-mediated peanut allergy. Approximately 72 participants will be randomized in this study to one of the five arms (randomization ratio of 2:2:2:1:1). Participants initially assigned to the 3-week placebo arm will receive the first dose of blinded remibrutinib treatment at the Day 22 visit. CCI. This is operationally handled by stratification to treatment arms based on CCI participation within the IRT system, and hence, not considered as a design parameter or confounding variable. The primary analysis will be conducted after all participants complete the end of study visit schedule.

CCI

CCI

CCI

## 1.2 Study objectives, endpoints and estimands

Table 1-1 Objectives and related endpoints

Objective(s)	Endpoint(s)
Primary objective(s)	Endpoint(s) for primary objective(s)

To evaluate the efficacy of oral remibrutinib CCI compared to placebo, as measured by the proportion of participants who can tolerate a single dose of <math>\geq 600</math> mg (1044 mg cumulative tolerated dose) of peanut protein without dose-limiting symptoms during the DBPCFC at one month

	

Responder status defined as tolerating a single dose of <math>\geq 600</math> mg (1044 mg cumulative tolerated dose) of peanut protein without dose-limiting symptoms during the DBPCFC conducted at one month

Secondary objective(s)	Endpoint(s) for secondary objective(s)


To evaluate the efficacy of oral remibrutinib CCI compared to placebo, as measured by the proportion of participants who can tolerate a single dose of <math>\geq 1000</math> mg (2044 mg cumulative tolerated dose) of peanut protein without dose-limiting symptoms during the DBPCFC at one month

To evaluate the efficacy of oral remibrutinib CCI compared to placebo, as measured by the proportion of participants who can tolerate a single dose of 3000 mg (5044 mg cumulative tolerated dose) of peanut protein without dose-limiting symptoms during the DBPCFC at one month

To evaluate the efficacy of oral remibrutinib CCI compared to placebo, as measured by the maximum symptom severity at any single challenge dose up to and including 1000 mg of peanut protein during the DBPCFC at one month

To evaluate the efficacy of 3 weeks of placebo treatment followed by 1 week of oral remibrutinib CCI treatment compared to one month of placebo treatment, as measured by the proportion of participants who can tolerate a single dose <math>\geq 600</math> mg of peanut protein without dose-limiting symptoms during the DBPCFC at one month

To evaluate the effects of multiple doses of remibrutinib compared to placebo (when applicable), as measured by multiple systemic biomarkers to inform on response to treatment or disease severity

	

Responder status defined as tolerating a single dose of <math>\geq 1000</math> mg (2044 mg cumulative tolerated dose) of peanut protein without dose-limiting symptoms during the DBPCFC conducted at one month

Responder status defined as tolerating a single dose of 3000 mg (5044 mg cumulative tolerated dose) of peanut protein without dose-limiting symptoms during the DBPCFC conducted at one month

Maximum severity of symptoms occurring at any challenge dose of peanut protein up to and including 1000 mg during the DBPCFC conducted at one month. Symptom severity will be categorized as 4 levels: None, Mild, Moderate, Severe

Responder status defined as tolerating a single dose of <math>\geq 600</math> mg (1044 mg cumulative tolerated dose) of peanut protein without dose-limiting symptoms during the DBPCFC conducted at one month (3 weeks of placebo + 1 week of remibrutinib treatment vs. one month of placebo)

Change from baseline at Weeks 1 and 4 of:

peanut-specific IgE, including peanut components

peanut-specific IgG4, including peanut components


Objective(s)	Endpoint(s)

To evaluate the safety and tolerability of multiple doses of remibrutinib

To assess the ability of remibrutinib to impact skin mast cells through the assessment of allergen-specific skin prick test (SPT)

To assess the pharmacokinetics (PK) of remibrutinib

	

Treatment-emergent adverse events, vital signs, ECG, and laboratory values, including immunoglobulin levels

Change from screening in SPT mean wheal diameters at one month

Remibrutinib concentrations in blood and PK parameters (including, but not necessarily limited to: Cmax, AUClast, AUCtau, Tmax)

Exploratory objective(s)	Endpoint(s) for exploratory objective(s)
CCI	

### 1.2.1 Primary estimand(s)

The estimand is the precise description of the treatment effect and reflects strategies to address events occurring during trial conduct which could impact the interpretation of the trial results (e.g. premature discontinuation of treatment). The primary clinical question of interest is to understand the treatment effect of remibrutinib over placebo among participants who have completed actual DBPCFC after one month (4-5 weeks) of treatment and regardless of intake of rescue medication prior to actual DBPCFC at one month.

The primary estimand is described by the following attributes to address the primary clinical question of interest:

- Population:** Participants aged 18 – 55 years, inclusive, who have been diagnosed with IgE-mediated confirmed peanut allergy and met study inclusion/exclusion criteria and have undergone actual DBPCFC (2A & B) at one month (4-5 weeks).
- Variable:** Responder status defined as tolerating a single dose of  $\geq 600$  mg (1044 mg cumulative tolerated dose) of peanut protein without dose-limiting symptoms during the DBPCFC conducted at one month (4-5 weeks). The cumulative tolerated dose is the sum of the tolerated doses, not including the reactive dose. Dose-limiting symptoms indicate a true allergic reaction occurring during administration of a single dose of peanut protein at the

actual DBPCFC that should preclude the administration of any further doses in the view of the investigator.

- **Treatment:** The randomized treatment (one of five arms specified in [Section 2.1.1.1](#)) plus rescue medication (e.g., epinephrine, short-acting beta agonist, and/or anti-histamines) prior to actual DBPCFC at one month, if needed.
- **Intercurrent events:**
  - Discontinuation of treatment prior to the End of Treatment Assessments on Days 25, 26 and 28: Participants who discontinue treatment prior to actual DBPCFC, or who miss more than 20% of treatment doses throughout the study, or who miss medication doses for  $\geq 3$  consecutive days in the seven days prior to the one month actual DBPCFC part 2A due to any reasons other than adverse events
  - Intake of rescue medication prior to the actual DBPCFC
- **Summary measure:** Difference in the proportion of responders between remibrutinib and placebo

Supplementary estimands to the primary estimand are defined in [Section 2.5.5](#).

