## **9 Discontinuation and completion**

### **9.1 Discontinuation from study treatment and from study**

#### **9.1.1 Discontinuation from study treatment**

Discontinuation of study treatment for a participant occurs when study treatment is stopped earlier than the protocol planned duration and can be initiated by either the participant or the investigator. The investigator must discontinue study treatment for a given participant if he/she believes that continuation would negatively impact the participant's well-being.

Study treatment must be discontinued under the following circumstances:

- Participant decision
- Pregnancy
- Any SAE, with the exception of anaphylaxis unrelated to study drug, and which does not require hospital admission for  $\geq 24$  hours.
- Any severe AE that is assessed to be at least possibly related to study drug
- Any moderate to severe infection
- Participant requires use of prohibited treatment as per [Section 6.2.2](#)
- Participant failure to comply with the study protocol results in potential risk to the participant
- Participant experiences a moderate or severe hypersensitivity event unrelated to the DBPCFC and suspected to be related to study treatment
- Confirmed QTcF  $> 500$  msec
- Abnormal liver laboratory results requiring discontinuation (see [Section 16.2](#))
- Abnormal renal laboratory results requiring discontinuation (see [Section 16.3](#))
- Platelets  $< 75,000/\text{mm}^3$
- Clinically significant spontaneous bleeding events
- Any other adverse event or laboratory abnormality that in the judgment of the investigator prevents the participant from safely continuing in the study
- Any protocol deviation or other situation that results in a significant risk to the participant's safety

If discontinuation of study treatment occurs, the investigator should make a reasonable effort to understand the primary reason for the participant's premature discontinuation of study treatment and record this information. If treatment code has been broken as noted in [Section 6.5](#) and [Section 6.7.3](#), and site personnel and sponsor determine discontinuation of study treatment is indicated, this information should be recorded. The investigator must also contact the IRT to register the participant's discontinuation from study treatment.

**All participants who discontinue from study treatment prematurely should complete the End of Study visit at the time of treatment discontinuation.**

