Participants who discontinue from study treatment and agree to participate in the post-study televisit, should be contacted as indicated in the Assessment Schedule ([Table 8-1](#)).

If the participant cannot or is unwilling to participate in the post-study televisit, the site staff should make every effort to maintain regular telephone contact with the participant, or with a person pre-designated by the participant. This telephone contact should at a minimum information on new/concomitant treatments and adverse events /serious adverse events should be obtained.

**Participants who discontinue study treatment will no longer undergo any DBPCFC that may be planned on the remaining visit(s).**

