### **16.4.2 DBPCFC Dosing schedule**

This study includes two DBPCFCs: the first at Screening (Visits 2 and 3), the second at the end-of-treatment (one month) (Day 26 and 28).

Each DBPCFC consists of two Parts, active allergen (peanut) challenge and placebo challenge. Each challenge is to be performed on a separate day (part 1A and 1B during screening, and part 2A and 2B at end-of-treatment period). The active allergen challenge is either given on the first day or the second day. To ensure and preserve the double-blind nature of the challenge, independent (unblinded) study site staff need to prepare the material for each challenge prior to administration. Study staff/investigator administering the challenge and Participants undergoing the challenge remain blinded to the identity of the challenge on the two test days (i.e. if peanut allergen or placebo is tested on the first or the second day). The time interval between each challenge is two to seven days; there must be a minimum of two full days and a maximum of 7 days between part 1A or 2A and part 1B or 2B DBPCFCs. There must be at least

72 hours between the completion of the DBPCFC part 1B and the first administration of study treatment at the randomization visit.

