### **2.5.3 Handling of intercurrent events**

The primary analysis will account for different intercurrent events as described below.

1. The primary analysis will be performed with completers only assuming dropouts occur completely at random. A completer is defined as a participant who completes DBPCFC after one month of study treatment or three weeks of placebo plus one week of study treatment. In other words, treatment policy strategy is applied here. Missing outcomes due to treatment discontinuation/interruption are assumed to occur at random and ignored.
2. Intake of rescue medication prior to DBPCFC conducted before one month: ignorable (treatment policy strategy, reflected in the Treatment attribute)

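### The SAP's primary population requires both challenge parts, so a peanut result observed on 2A can be lost when 2B is not done, even when that result is a failure

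*SAP*

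**What the plan says.** **Population.** SAP 1.2.1 restricts the primary estimand to participants who "have undergone actual DBPCFC (2A & B) at one month (4-5 weeks"). Protocol 2.1 asks only that the one-month DBPCFC was undergone. The explicit reference to both parts appears in the SAP, while SAP section 4 reports no change from the protocol's analyses.

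**Analysis.** SAP 2.5.3 states: "The primary analysis will be performed with completers only assuming dropouts occur completely at random". It adds: "A completer is defined as a participant who completes DBPCFC after one month of study treatment" (or after three weeks of placebo plus one week of active treatment). It then labels this a treatment-policy strategy and says that outcomes missing because treatment was stopped or interrupted are ignored.

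**Challenge.** Protocol 16.4.2: "Each DBPCFC consists of two Parts, active allergen (peanut) challenge and placebo challenge". On the order: "The active allergen challenge is either given on the first day or the second day". The order is assigned through IRT (Protocol 6.4.2). The responder variable in SAP 1.2.1 concerns peanut protein only.

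**How 2B can be lost after 2A.** Protocol 9.1.1: "Participants who discontinue study treatment will no longer undergo any DBPCFC that may be planned on the remaining visit(s"). Its reasons for stopping treatment include the participant's own decision and "Any SAE, with the exception of anaphylaxis unrelated to study drug, and which does not require hospital admission for" 24 hours or more.

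**The concern.** A participant challenged with peanut on 2A has a final primary outcome that day. The 2B visit is then the placebo challenge, which does not enter the responder definition. If 2B is not done, the two-part population and the completer rule together remove a result that has already been observed.

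The damaging case is a peanut failure on 2A followed by no 2B. The exclusion is then caused by the outcome, which is the opposite of completely-at-random dropout. It also does not fit a treatment-policy strategy, which would use the observed 2A result whatever happened afterwards.

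At stake are the arm response rates that feed the MCP-Mod dose-response fit, which SAP 2.5 says will support the choice of Phase 3 dose. The size of the upward shift depends on the true rate, so the doses are not affected equally. Two programmers could also reach different denominators, because the PD analysis set in SAP 2.2 would admit the 2A result and the estimand population would not.

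**Working it through.** **The plan's own figure.** Protocol 12.8 gives 72 participants, 2:2:2:1:1 allocation and about 10% discontinuation.
- Each 1-month arm: 72 × 2/8 × 0.9 = 16.2. The plan says 14 to 16.
- Placebo and 1-week arms: 72 × 1/8 × 0.9 = 8.1 each. The plan says 7 to 8.

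The upper ends are reproduced. The lower ends (14 of 18, 7 of 9) correspond to 22% loss. The stated power of at least 80% cannot be reproduced because the doses, model shapes and placebo rate are redacted.

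**Inputs for the effect of the rule**
- p, true response rate: 80% for remibrutinib is the one visible design value (Amendment 02 rationale). Other values are illustrative.
- s, share with peanut on 2A: 0.5, an assumption; the order ratio is not stated.
- q, chance that a 2A peanut failure has no 2B: not in the documents; 0.10 to 0.50 shown.
- 2A tolerators are assumed to return for 2B.

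**Formulas.** Share dropped d = s(1 − p)q. Observed rate = p / (1 − d).

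Example, p = 0.40 and q = 0.50: d = 0.5 × 0.6 × 0.5 = 0.15, and 0.40 / 0.85 = 47.1%.

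| True rate | q = 0.10 | q = 0.25 | q = 0.50 |
|---|---|---|---|
| 5% | 5.2% | 5.7% | 6.6% |
| 20% | 20.8% | 22.2% | 25.0% |
| 40% | 41.2% | 43.2% | 47.1% |
| 80% | 80.8% | 82.1% | 84.2% |

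**Numbers dropped.** Of 16 in an active arm with an 80% rate: 16 × 0.01 = 0.2 at q = 0.10 and 16 × 0.05 = 0.8 at q = 0.50. With a 40% rate: 16 × 0.03 = 0.5 and 16 × 0.15 = 2.4. Of 8 on placebo with a 5% rate, 7.6, 7.0 and 6.1 remain at the three values of q. The power statement relies on 7.

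**Change in the difference, remibrutinib 80%**

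| Placebo rate | q = 0.10 | q = 0.25 | q = 0.50 |
|---|---|---|---|
| 5% | +0.6 points | +1.4 | +2.7 |
| 20% | 0.0 | −0.2 | −0.8 |
| 40% | −0.4 | −1.2 | −2.8 |

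At the extreme q = 1 the three rows reach +4.4, −4.4 and −8.3 points.

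**Check on the mechanism.** If 2A tolerators missed 2B at the same rate q, the observed rate would be p(1 − sq) / (1 − sq) = p. Participants would be lost but the arm rate would not shift. The bias comes from loss that follows failure.

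**The case against.** **The exclusion is inferred.** No sentence names the case of 2A without 2B. SAP Tables 2-1 and 5-2 do not list it, and the PD analysis set asks only for available PD data. The reference to 2A and 2B might simply identify the end-of-treatment challenge as against the screening one. Protocol 16.4.7 speaks of completing the DBPCFC when it means a single challenge day. This stands as a limit on certainty: the team may intend to keep these results. It does not remove the problem, because the population and completer definitions, with the two-part definition of a DBPCFC, point to exclusion.

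**The route is narrow.** A reader might infer that a serious peanut reaction on 2A routinely ends treatment and cancels 2B. Protocol 9.1.1 does not support that. It exempts anaphylaxis unrelated to study drug without a long admission, and its hypersensitivity criterion concerns events unrelated to the challenge. A positive 2A does not in itself cancel 2B. Participants have also already reacted to peanut at screening and completed both screening parts. This stands, and it suggests a low q.

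**The upper values of q are high for this plan.** At 5% placebo response, q = 0.25 and 0.50 imply 11.9% and 23.8% placebo loss from this cause alone, against about 10% expected overall. At 80%, a shift of up to about 4 points is small beside a standard error of √(0.8 × 0.2 / 16) = 10 points. Both points stand.

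**It may already be covered.** Supplementary estimand 2 (SAP 2.5.5) counts a missing DBPCFC as non-response, apart from public health emergencies. It does not say whether a missing 2B alone counts as missing, and it leaves the primary analysis unchanged.

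**Conclusion.** The point holds as a defect in the primary definitions. Taken literally, they discard an observed peanut result when the placebo part is not done. Where that result is a failure, the denominator depends on the outcome, against both the dropout assumption and the treatment-policy label in SAP 2.5.3.

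The effect is probably small. With peanut on 2A for half and 10% to 50% of 2A failures missing 2B, an 80% rate is overstated by about 1 to 4 points and a 40% rate by about 1 to 7. The return rate after a 2A failure is not in the documents.

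A reader might infer that the bias favours remibrutinib. The documents do not establish this. It is so at a placebo rate near 5%, which the visible historical rows in SAP Table 2-2 suggest (7/164 = 4.3%). But the design placebo rate is redacted, and at 20% to 40% against 80% the difference is unchanged or shrinks. What can be said is that, under these assumptions, the rule raises the observed rate in every arm, by an amount that varies with the true rate.

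**What to change.** In SAP 1.2.1 and 2.5.3, before final database lock:

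1. Define the primary population and the completer by an evaluable peanut part, 2A or 2B according to the IRT sequence. The deviations in Table 2-1 that set a challenge result to missing continue to apply.
2. Use the observed peanut result whether or not the placebo part was done. Dose-limiting symptoms at or before the 600 mg dose are a non-response. A participant who tolerated at least 600 mg on 2A and missed 2B is a responder.
3. Report the number of one-part participants by arm and challenge order.
4. Keep the placebo part for supplementary estimand 4, and say in supplementary estimand 2 whether a missing placebo part alone counts as a missing DBPCFC.

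The cost is SAP wording and one extra count table. No visit, challenge procedure or treatment rule changes.
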